## NEWS score calculation

Criteria	Point Value
Respiratory Rate (breaths per minute)	
≤8	+3
9-11	+1
12-20	0
21-24	+2
≥25	+3
Oxygen Saturation (%)	
≤91	+3
92-93	+2
94-95	+1
≥96	0
Any Supplemental Oxygen	
Yes	+1
No	0
Temperature in °C (°F)	
≤35.0 (95)	+3
35.1-36.0 (95.1-96.8)	+1
36.1-38.0 (96.9-100.4)	0
38.1-39.0 (100.5-102.2)	+1
≥39.1 (≥102.3)	+2
Systolic BP	
≤90	+3
91-100	+2
101-110	+1
111-219	0
≥220	+3

**Heart Rate (beats per minute)**

≤40	+3
41-50	+1
51-90	0
91-110	+1
111-130	+2
≥131	+3

**AVPU (Alert, Voice, Pain, Unresponsive)**

A	0
V, P, or U	+3

- A low score (NEWS 1–4) should prompt assessment by a competent registered nurse who should decide if a change to frequency of clinical monitoring or an escalation of clinical care is required.
- A medium score (i.e. NEWS of 5–6 or a RED score) should prompt an urgent review by a clinician skilled with competencies in the assessment of acute illness – usually a ward-based doctor or acute team nurse, who should consider whether escalation of care to a team with critical-care skills is required (i.e. critical care outreach team).
- A RED score refers to an extreme variation in a single physiological parameter (i.e., a score of 3 on the NEWS chart in any one physiological parameter, colored RED to aid identification; e.g., heart rate)
- A high score (NEWS ≥7) should prompt emergency assessment by a clinical team/critical care outreach team with critical-care competencies and usually transfer of the patient to a higher dependency care area.

#### 4. Version History

Version	Summary of Changes	Author(s)/Title
1.0, 24 Jan, 2018	Not Applicable, New Document	
2.0, 19 Jun, 2019	
Title Page: Updated address for Covidien Services Europe
 
Section 2: Updated address for Covidien Services Europe. Updated expected total patient recruitment from 300 to 210; 70 to be recruited in Phase I and 140 in Phase II. Updated Inclusion criteria No. 1 to indicate that patients may be enrolled if the they have POSPOM score <math>\geq 24</math> OR ARISCAT score <math>\geq 26</math>.
 
Section 5: Updated expected total patient recruitment from 300 to 210; 70 to be recruited in Phase I and 140 in Phase II. Indicated that sites will have at least one month, as opposed to one week to familiarize themselves unblinded devices. Updated Figure 1 to reflect the above.
 
Section 7.3: Updated Inclusion criteria No. 1 to indicate that patients may be enrolled if the they have POSPOM score <math>\geq 24</math> OR ARISCAT score <math>\geq 26</math>.
 
Section 8.7: Updated to indicate that the point of patient exit from the study will not be the end of the monitoring period, but instead upon discharge from the hospital. Clarified that AEs are reportable during this period.
 
Section 8.8: Updated to indicate that Date of patient discharge from hospital should be collected at study exit.
 
Section 12.1: Updated total patient population from 300 to 210.

## 1. Version History

Version	Summary of Changes	Author(s)/Title
Version 1.0	Not Applicable, New Document	[REDACTED]
Version 1.1	Updated accordingly to align with CIP version 2.0	[REDACTED]

## 2. List of Abbreviations and Definitions of Terms

Abbreviation	Definition
AE	Adverse Event
CIP	Clinical Investigation Plan
CS	Capnostream
EC	Ethics Committee
EtCO 2	End Tidal CO 2
EWS	Early Warning Scores
FAS	Full Analysis Set
FN	False Negative
FP	False Positive
GEE	Generalized Estimating Equation
ICF	Informed Consent Form
ICH	International Conference on Harmonization
ICH E3	ICH guideline E3: Structure and content of clinical study reports
ICH E6	ICH guideline E6: Guideline for Good Clinical Practice
ICH E9	ICH guideline E9: Statistical principles for clinical trials
ICU	Intensive Care Unit
IPI	Integrated Pulmonary Index
NPV	Negative Predictive Value
OC	Oracle Clinical
OR	Odds Ratio
PPS	Per Protocol Set
PPV	Positive Predictive Value
RC	Respiratory Compromise
RR	Respiratory Rate
SAE	Serious Adverse Event
SAP	Statistical Analysis Plan
SOPs	Standard Operating Procedure
SpO 2	Pulse Oximetry
TLF	Tables, Listings, and Figures
TN	True Negative
TP	True Positive

### 3. Introduction

Early postsurgical period is associated with high incidence of postoperative pulmonary complications, including pneumonia, aspiration pneumonitis, respiratory failure, re-intubation within 48h, weaning failure, pleural effusion, atelectasis, bronchospasm, and pneumothorax.

The most frequent severe postoperative respiratory complications is respiratory failure, defined as unexpected tracheal re-intubation, need for postoperative mechanical ventilation, postoperative acute lung injury and acute respiratory distress syndrome.

Current standard of care for respiratory monitoring of hospital ward high risk patients, such as those receiving opioid therapy, is intermittent documentation of SpO2 value. Respiratory rate (RR) is often determined by clinician assessment though manual inaccurate respiration counts.

There are no data on the real incidence and severity of potential RC markers and their correlation with cardiopulmonary or other complications in European postsurgical patients. A pilot study on this topic could be useful to collect information on the utility of continuous SpO2 and capnography monitoring in this setting and to develop future clinical evidence.

The main purpose of the LIFEGUARD study is to quantify the incidence and the severity of postoperative RC markers on high risk postsurgical patients on a general ward.

This SAP is based on Protocol 2.0, 19 Jun 2019 titled, “**LIFEGUARD Study** – Continuous Respiratory Monitoring on the General Ward”. The SAP has been prepared in agreement with Medtronic internal procedures and using the CONSORT Flow diagram^1 and International Conference on Harmonization (ICH) guidelines ICH E3, ICH E6 and ICH E9 as guidelines.

### 4. Study Objectives

#### 4.1. Primary Objective

The primary objective of this study is to quantify the incidence of RC markers in high risk postsurgical patients, using a system comprised of two continuous monitoring devices, connected to a remote monitoring platform.

The occurrence of at least one of the following RC markers will be considered as primary endpoint for patients monitored by Capnostream 20p during both study Phases:

- SpO2 ≤ 90% for ≥ 3 minutes (or SpO2 ≤ 90% for < 3 min with an action taken);
- RR ≤ 8 or ≥ 22 bpm for ≥ 3 minutes (or RR ≤ 8 or ≥ 22 bpm for < 3 min with an action taken);
- EtCO2 ≤ 15 or ≥ 60 mmHg for ≥ 3 minutes (or etCO2 ≤ 15 or ≥ 60 mmHg for < 3 min with an action taken);
- Apnea episode lasting > 30 seconds.

The occurrence of at least one of the following RC markers will be considered as primary endpoint for patients monitored by PM1000N during both study Phases:

- SpO2 ≤ 90% for ≥ 3 minutes (or SpO2 ≤ 90% for < 3 min with an action taken);

- RR  $\leq$  8 or  $\geq$  22 bpm for  $\geq$  3 minutes (or RR  $\leq$  8 or  $\geq$  22 bpm for < 3 min with an action taken).

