## 6. Determination of Sample Size

The sample size calculation is based on primary endpoint and it was estimated using data from previous studies with a precision-based calculation. Recent data on post-surgical patient have shown a proportion of patient with the RC markers for the  $\text{SpO}_2 \leq 85\%$  for  $\geq 3$  minutes at 13% and for  $\text{RR} \leq 8$  or  $\geq 22$  bpm for  $\geq 3$  minutes at 1.4% in patients undergoing opioid therapy. Using this information, a minimum proportion of 10% of patients with RC markers with a sample size of 182 subjects will be able to obtain a 95% confidence level with a precision of 5% (ranging from 5% to 10%) and a power of at least 0.80 defined as the probability of achieving the desired precision. Considering a 10% withdrawal or potential dropouts and a potential attrition rate to monitoring compliance of 5% a total of approximately 210 subjects will be enrolled. This cohort will be used prospectively for the blinded and not blinded phase with a ratio 1:2 respectively to minimize not blinded monitored subjects. The blinded phase will enroll

70 subjects randomly allocated 1:1 in the Capnostream 20p and PM1000N arms while the not blinded phase will enroll 140 subjects with same randomized schedule.

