## 7.9. Evaluation of Objectives

### 7.9.1. Primary Endpoint

The Primary Endpoint of the Study is to quantify the incidence of RC markers in high risk postsurgical patients, using a system comprised of two continuous monitoring devices, connected to a remote monitoring platform. The proportion and rate of “At least one RC marker” event will be calculated and reported.

The “At least one RC marker” event is defined as the occurrence of at least one of the following RC markers:

1.  $\text{SpO}_2 \leq 90\%$  for  $\geq 3$  minutes (or  $\text{SpO}_2 \leq 90\%$  for  $< 3$  min with an action taken);
2.  $\text{RR} \leq 8$  or  $\geq 22$  bpm for  $\geq 3$  minutes (or  $\text{RR} \leq 8$  or  $\geq 22$  bpm for  $< 3$  min with an action taken);
3.  $\text{EtCO}_2 \leq 15$  or  $\geq 60$  mmHg for  $\geq 3$  minutes (or  $\text{EtCO}_2 \leq 15$  or  $\geq 60$  mmHg for  $< 3$  min with an action taken);
4. Apnea episode lasting  $> 30$  seconds.

For patients monitored by PM1000N, only RC markers #1 and #2 will be considered.

RC determination will be assessed by a physician belonging to the “other” site (cross assessment by the sites). This assessment will be made by the analysis of both device and clinical data for each patient. For each patient all potential RC episodes will be derived using the Detection Tool (see Section 10.1) and will be submitted to the other site’s physician in order to adjudicate the potential RC episodes starting from episodes most likely to be RC. The adjudication will stop at the first RC occurring per patient.

The Events’ rates will be computed as (total number of “At least one RC marker” event)/(total number of time-person in PPS) and will be reported separately for each arm and phase of the study. Events’ rates will be displayed together with their 95% confidence interval (95%CI).

If the number of episode per patient result unbalanced, adjusted rates will be reported using the GEE model, together with their 95% confidence interval (95%CI).

If appropriate, also the events’ rates for each RC marker will be reported separately, for each arm and phase of the study.

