### 7.9.2. Secondary Endpoints

The secondary endpoints are:

1. To compare phases in terms of Primary endpoint incidence;
2. To compare phases in terms of respiratory and SAE incidence, number of ICU transfers and related length of stay, Code blues and RRT responses.
3. To evaluate the rate of clinical early interventions performed by nurse staff to prevent a potential AE, introducing continuous monitoring devices connected to a remote monitoring platform;
4. To evaluate the nurses’ satisfaction related to the monitoring system introducing continuous monitoring devices connected to a remote monitoring platform;
5. To establish the Predictive values of  $\text{EtCO}_2$ , RR,  $\text{SpO}_2$ , plethysmography-derived RR, IPI and EWS in respect to respiratory and other SAE.

In order to evaluate secondary **endpoints #1 and #2**, the incidence of events will be reported together with the comparison between phases, by means of the Chi-square test or Fisher exact test for extreme

proportions, as appropriate. If the monitoring/study exposure results different between phases, also the rates of events will be reported, together with the 95% Poisson Confidence Intervals. The Poisson regression model will be used to calculate the Incidence Rate ratio (IRR), with the d-scale option.

For **endpoint #3**, the rate of clinical early interventions will be calculated as (number of early interventions)/(total time-person in FAS) and it will be reported together with the 95% Poisson Confidence Interval.

Early interventions include, as defined in CRF (Monitoring Period):

1. Stimulated subject to breathe;
2. Repositioned/opened airway;
3. Held or reduced Respiratory Depressive (RD);
4. Added or increased supplemental oxygen;
5. Ventilation support;
6. Other

**Endpoint #4** will be evaluated reporting a summary of the nurses' satisfaction answers.

To identify the predictive values for EtCO2, RR, SpO2, plethysmography-derived RR, IPI and EWS, which can predict respiratory and other SAE, a sensitivity analysis will be performed (**endpoint #5**), and the following parameters will be reported, for each RC marker:

1. **Sensitivity** = 
$$\frac{(\# \text{ of clinical events "Yes" and with RC marker "Yes"})}{(\# \text{ of clinical events "Yes"})} = \frac{TP}{(TP+FN)}$$
2. **PPV** = 
$$\frac{(\# \text{ of clinical events "Yes" and with RC marker "Yes"})}{(\# \text{ of events with RC marker "Yes"})} = \frac{TP}{(TP+FP)}$$

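### The SAP counts excursions under 3 minutes with an action towards the primary endpoint; the protocol does not, and alarm-triggered actions exist only in Phase II

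*SAP*

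**What the plan says.** **Protocol.** Section 4.1.1 (and the Synopsis) defines the SpO2, RR and, for Capnostream, etCO2 markers by a threshold held for at least 3 minutes. Capnostream patients also have apnea beyond 30 seconds. Staff action plays no part. Section 8.10 makes device memory the source for the number and duration of markers.

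**SAP.** Section 3 states: "This SAP is based on Protocol 2.0, 19 Jun 2019". The Version History entry for version 1.1 reads "Updated accordingly to align with CIP version 2.0". Yet section 4.1 adds to the SpO2, RR and etCO2 markers, for both devices where applicable and for both phases, an alternative of the form "or RR ≤ 8 or ≥ 22 bpm for < 3 min with an action taken". Section 7.9.1 repeats it in the definition used for analysis. Section 7.12, on changes to the planned analysis, covers only the 24-hour and 90% cut-offs.

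**Phases.** Phase I alarms are silenced and screens blinded (Protocol 8.7). Protocol 4.1.2 and SAP 4.2 expect only non-alarm-triggered interventions in Phase I, and both kinds in Phase II. Appendix B's recommended Phase II alarms use the endpoint's SpO2, RR and etCO2 thresholds after more than 30 seconds; sites may modify them.

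**Comparison and adjudication.** For secondary endpoints #1 and #2, SAP 7.9.2 says "the incidence of events will be reported together with the comparison between phases", by chi-square or Fisher test. Candidates are adjudicated by a physician at the other site: "This assessment will be made by the analysis of both device and clinical data for each patient". Those thought likeliest to be RC go first, and "The adjudication will stop at the first RC occurring per patient".

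**The concern.** There are two separate problems.

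1. **Two primary endpoints.** An analyst who follows the SAP reports an incidence that is not the protocol's. Nothing marks the clause as a departure, and no duration-only sensitivity analysis is planned.

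2. **A route that is more open in one phase.** In Phase II an alarm can sound, and staff can act, while an excursion is still under 3 minutes. That action can itself turn the excursion into an endpoint event. In Phase I only an action taken for some other reason can do so. Secondary endpoint #1 then compares the phases on an outcome that the intervention can trigger.

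Two gaps make this harder to control. SAP 7.9.2 lists early interventions, ending in an open category, but 4.1 and 7.9.1 do not say whether that list defines an action. Adjudication draws on clinical data and is not stated to be blind to phase, so it does not clearly remove the asymmetry.

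**Working it through.** **Step 1. Definitions side by side**

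| Patient has | Protocol 4.1.1 | SAP 4.1 / 7.9.1 |
|---|---|---|
| SpO2, RR or etCO2 excursion of at least 3 min | counts | counts |
| Apnea over 30 s (Capnostream) | counts | counts |
| Excursion under 3 min, no action | no | no |
| Excursion under 3 min, action taken | no | **counts** |

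The last row is the mismatch. It needs no assumption.

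**Step 2. The plan's own figure.** The plan gives no figure for this clause. SAP 6 works "with a sample size of 182 subjects", and 182 × 1.15 = 209.3, which agrees with about 210 enrolled. That precision calculation does not use the clause and does not change with it. Split 1:2, 182 gives about 61 v 121 with devices pooled, or about 30 v 60 in one arm. Both are shown because SAP 7.9.2 does not say whether arms are pooled, while Protocol 12.3 describes phase comparisons within groups.

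**Step 3. Illustration of the asymmetry (all rates assumed).** Let b be the share of patients with a qualifying long marker, q the share whose only candidates are short, a1 and a2 the Phase I and Phase II probabilities that such a patient has an action, and k the share of these accepted at adjudication.

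- Observed share in phase j = b + q × aj × k
- Difference with no true effect = q × k × (a2 − a1), which is zero if the action rates are equal

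Take b = 0.37. This is borrowed from Protocol 3.1, where it describes SpO2 below 90% for over an hour, so the true base may be higher. The probability of rejection by the two-sided 5% Pearson chi-square test comes from exact enumeration of all tables. With equal definitions it is 5.1% pooled and 5.2% in one arm.

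| q | a1 v a2 | Observed, k = 1 | Rejection, k = 1 (pooled / one arm) | Rejection, k = 0.5 |
|---|---|---|---|---|
| 0.10 | 0 v 0.25 | 37.0 v 39.5% | 6.2 / 5.7% | 5.3 / 5.3% |
| 0.20 | 0.10 v 0.50 | 39.0 v 47.0% | 16.9 / 10.7% | 7.9 / 6.5% |
| 0.30 | 0.25 v 0.50 | 44.5 v 52.0% | 15.2 / 9.8% | 7.3 / 6.2% |
| 0.30 | 0 v 0.50 | 37.0 v 52.0% | 47.4 / 26.1% | 15.7 / 10.3% |
| 0.30 | 0 v 0.75 | 37.0 v 59.5% | 81.9 / 51.9% | 29.3 / 16.8% |

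Example, second row: 0.37 + 0.20 × 0.10 = 0.39 and 0.37 + 0.20 × 0.50 = 0.47.

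Here q is a share of all patients. If it is instead a share of those without a long marker (q × 0.63), the pooled range of 6.2–81.9% becomes 5.5–43.2%.

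**Step 4. The duration-only definition under alarm response.** Suppose monitoring prevents no onset, but staff end a share c of the long episodes before 3 minutes. The Phase II share becomes 0.37 × (1 − c).

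- c = 0.25: 37% v 27.75%; a significant reduction is reported 25.4% of the time pooled, 14.8% in one arm.
- c = 0.50: 37% v 18.5%; 77.4% pooled, 48.6% in one arm.

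Only the two observed shares enter the test, so an equal fall caused by real prevention gives the same figures. The endpoint cannot tell the two apart.

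**Step 5. Adjudication.** The stop rule means that once a short action-qualified episode is accepted, a long episode in the same patient goes unreviewed. Taking the likeliest candidates first makes this less probable, but the ranking is undefined and does not guarantee that long episodes lead.

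**The case against.** The strongest reply is that the clause has a sensible purpose. An excursion that staff treat at 2 minutes did occur, and the primary objective is to quantify incidence. Dropping it means that alarm response lowers the Phase II count even if no onset is prevented, as Step 4 shows. This stands. It means that neither version alone separates prevented episodes from episodes treated early. It supports reporting both, but does not justify replacing the protocol's endpoint without saying so.

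The protocol also uses action elsewhere: in judging whether an alarm mattered (8.7) and whether a marker is an adverse event (10). However, Appendix A says that a marker without symptoms or invasive action still meets the primary endpoint, so action is not part of that definition.

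The consequence is limited. The primary analysis is descriptive. The affected test is secondary, sequential, non-randomised and unadjusted for multiplicity, in a pilot. SAP 7.9.2 also plans Poisson rate ratios if exposure differs, which Step 3 does not model. Protocol 12.2 requires deviations to be justified in the final report, but that comes after the data and does not settle the definition beforehand.

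A reader might infer that the clause hides a true reduction and so biases the study against monitoring. The documents do not support that. It treats duration-only as the truth, when that version can show a reduction made up only of episodes cut short. A reader might also infer that the protocol's endpoint is lost. That goes too far: device memory keeps marker number and duration, so the risk is confined to the adjudicated data.

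**Conclusion.** The mismatch is certain and rests on the text alone: the SAP's primary endpoint is broader than that of the protocol it claims to follow, and no reason is given. That is enough to require correction before analysis.

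That the added route is wider in Phase II follows from the design, since alarm-triggered actions are planned only there. Whether the Phase II count rises relative to Phase I depends on short excursions being acted on more often in Phase II. Non-alarm actions can also qualify in Phase I, and with equal action rates the spurious difference is zero.

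The size is unknown. The percentages in Step 3 run from near nominal to very large, depending on rates that the documents do not give. They show what is possible and should not be cited as expected error rates.

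**What to change.** In the SAP:

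- **4.1 and 7.9.1.** Restore the protocol's definition (at least 3 minutes, plus apnea over 30 seconds for Capnostream) as the headline primary estimate and for secondary endpoint #1.
- **Alongside it, for both analyses.** Prespecify the action-inclusive version by arm and phase, split into alarm-triggered and non-alarm-triggered actions.
- **Interpretation.** State that the two versions answer different questions, and that a phase difference seen in only one of them is not to be read as a benefit or harm of monitoring.
- **Action.** State which items of the 7.9.2 early-intervention list count.
- **Adjudication order.** Review candidates of at least 3 minutes and apnea candidates first, and stop if one is accepted; that patient counts under both versions. Go on to short candidates with an action only if none is accepted.

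**Cost.** This is SAP wording. The headline needs no new data, since device memory already gives durations (Protocol 8.10). The supplementary count uses the number and type of interventions already collected (Protocol Table 2). Adjudicators review a few extra episodes. The downside is that episodes cut short by staff leave the headline count, but they remain tabulated.

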## 4.2. Secondary Objectives

The study secondary objectives are the followings:

1. To compare the two study Phases (see Section 7.1.1) in terms of primary endpoint incidence;
2. To compare the two study Phases in terms of respiratory AEs and SAE incidence, numbers of ICU transfers and related length of stay, Code blues and RRT responses;
3. To evaluate the impact of introducing continuous monitoring devices connected to a remote monitoring platform on the clinical workflow, defined as the rate of clinical early interventions performed by nurse staff to prevent a potential AE (e.g. patient stimulation, Jaw thrust maneuver, oxygen administration started or increased, medication change, etc.);
4. To evaluate the impact of introducing continuous monitoring devices connected to a remote monitoring platform on clinical staff's workflow, defined as nurses' satisfaction related to the monitoring system;
5. To characterize the predictive values of EtCO2, RR, SpO2, plethysmography-derived RR, IPI and EWS in respect to respiratory and other SAE.

Related secondary objectives are:

1. Incidence of RC markers recorded by the monitoring system during each Phase;
2. Incidence of respiratory AEs and SAE, number of ICU transfers and related length of stay, Code blues and RRT responses recorded in the two study Phases;
3. Average rate of early interventions for patient will be calculated in both study Phases. In Phase I there should only be non- alarm-triggered interventions, as in clinical practice, while in Phase II there should be two sub-groups of clinical early interventions: alarm-triggered and non- alarm-triggered;
4. Clinical staff's satisfaction related to the monitoring system's introduction in their current workflow will be evaluated through a survey performed at the end of the study;
5. Sensitivity and specificity of each monitored parameter in predicting and identifying respiratory and SAE will be calculated. EWS will be the only parameter not automatically collected by the monitoring system but manually collected.

